2 STUDY OBJECTIVES

Primary Objective:

The primary objective of this study is to assess anti-tumor activity of Leronlimab (PRO 140) in the treatment of patients with CCR5+ locally advanced or metastatic solid tumors.

Secondary Objectives:

[figure not shown]
The secondary objectives of this study are:

- To collect further safety, tolerability and efficacy data.
- To evaluate correlative studies for better treatment selection in future validation studies

3 STUDY DESIGN

This is a multicenter study that will enroll up to 30 subjects. The target population for this study is subjects with histologically or cytologically confirmed diagnosis of CCR5+, locally advanced or metastatic solid tumors. A study flow schematic is presented in **Figure 3-1**.

Figure 3-1: Study Schematic

Note: Scans are to be done approximately every 3 months or according to institution's standard practice by CT, PET/CT or MRI with contrast (per treating investigator's discretion) using the same method as at baseline.

This is a single arm study with 30 patients of leronlimab (PRO 140) patients with CCR5+ locally advanced or metastatic solid tumors.

Leronlimab (PRO 140) will be administered subcutaneously as weekly dose of 525 mg until disease progression or intolerable toxicity. Subjects participating in this study will be allowed to receive/continue standard-of-care chemotherapy or radiotherapy as per the dosing schedule included on the package insert.

Patients will be evaluated for tumor response approximately every 3 months or according to institution's standard practice by CT, PET/CT or MRI with contrast (per treating investigator's

discretion) using the same method as at baseline. Tumor measurements will be done using RECIST v1.1.

Note: Subjects participating under Protocol version 1.0 received 350 mg of PRO 140. Dose was increased from 350 mg to 525 mg weekly under version 2.0 of this protocol.

Subjects enrolled under version 1.0 have the option of remaining on their current dose of 350mg or increasing their dose to 525 mg for the remainder of the trial.

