Name of Study Product: Leronlimab (PRO 140) - Humanized monoclonal antibody to CCR5	
Protocol Number: CD09_Basket	Indication: Locally Advanced or Metastatic Solid Tumors
Title of Study: Basket Study of Leronlimab (PRO 140) in Patients with Advanced and/or Metastatic Solid Tumors	
Planned Number of Subjects: 30 Subjects	Study Development Phase: Phase II
Study Population: Patients with CCR5-positive, locally advanced or metastatic solid tumors.	
Objectives: Primary Objective: The primary objective of this study is to assess anti-tumor activity of Leronlimab (PRO 140) in the treatment of patients with CCR5-positive, locally advanced or metastatic solid tumors as part of a defined treatment protocol. Secondary Objectives: The secondary objectives of this study are: 
• To collect further safety, tolerability and efficacy data.• To evaluate correlative studies for better treatment selection in future validation studies.	
Trial Design: This is a single arm study with 30 patients of leronlimab (PRO 140) in patients with CCR5+ locally advanced or metastatic solid tumors. Leronlimab (PRO 140) will be administered subcutaneously as weekly dose of 525 mg until disease progression or intolerable toxicity. Subjects participating in this study will be allowed to receive/continue standard-of-care chemotherapy or radiotherapy as per the dosing schedule included on the package insert. In this study, patients will be evaluated for tumor response approximately every 3 months or according to institution's standard practice by CT, PET/CT or MRI with contrast (per treating investigator's discretion) using the same method as at baseline. Tumor measurements will be done using RECIST v1.1. The total study duration for each subject consists of pre-screening, screening, treatment, and follow-up	

Name of Sponsor/Company: CytoDyn, Inc.	
Name of Study Product: Leronlimab (PRO 140) - Humanized monoclonal antibody to CCR5	
Protocol Number: CD09_Basket	Indication: Locally Advanced or Metastatic Solid Tumors
periods. A study flow diagram is presented in Figure 4-1 .	

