1.5 DOSE RATIONALE

Leronlimab (PRO 140) is currently under development for the indication of HIV in combination with other antiretroviral agents or as single agent maintenance therapy for the treatment of only CCR5-tropic human immunodeficiency virus type 1 (HIV-1) infection. The safety profile of leronlimab (PRO 140) has been extensively evaluated in clinical trials of HIV-positive patients. PRO 140 has been administered intravenously or subcutaneously to more than 750 healthy and HIV-1 infected individuals in Phase I/II/III studies. The drug has been well tolerated following intravenous administration of single (or multiple) doses of 0.5 to 10 mg/kg or up to 700 mg weekly doses as subcutaneous (SC) injection. Overall, 324 subjects have been exposed to PRO 140 350 mg SC weekly dose with the longest duration of exposure lasting 4 years. Similarly, more than 250 and 150 subjects have been exposed to PRO 140 525 mg and 700 mg SC weekly dose, respectively. No dose-proportional increases in incidence and severity of AEs were reported at the 700 mg dose compared to the 525 mg and 350 mg dose levels of PRO 140 (leronlimab).

We anticipate a manageable safety profile with combination therapy since: 1) Leronlimab (PRO 140) is not metabolized by the liver, and therefore may have the potential for a better tolerability profile than many of the existing small-molecule therapies; 2) Unlike small molecules, monoclonal antibodies are too large to be filtered by the kidneys and are not eliminated in the urine, except in pathologic conditions. If low molecular weight antibody fragments are filtered, they are usually reabsorbed and metabolized in the proximal tubule of the nephron. These pharmacodynamic characteristics and current safety profile led to the selection of 350 mg of leronlimab (PRO 140) as the starting dose in combination with other chemotherapy agents.

Note: Based on successful safety data review for the first three subjects enrolled in CD07_TNBC Study in Cohort A (350 mg leronlimab SC weekly + AUC 5 Carboplatin every 3 weeks), dose escalation to proceed with enrollment of subjects under Cohort B (525 mg leronlimab SC weekly + AUC 5 Carboplatin every 3 weeks). The similar dose change of Leronlimab in combination with other chemotherapy agents is now implemented under the current protocol version for the CD09_Basket Study.

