1.6.2. Intended Benefit for Subjects

This study provides an opportunity for subjects with CCR5 + locally advanced or metastatic solid tumors to have once weekly SC treatment with leronlimab (PRO 140) in combination with standard-of-care chemotherapy or radiotherapy. Subjects participating in the present study will contribute to the development of a drug which has the potential to become a treatment option for them and others in the future.

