3.3 ELIGIBILITY CRITERIA

3.3.1. Inclusion Criteria

Subjects are required to meet all of the following criteria for enrollment into the study:

1. Must have a histologically or cytologically confirmed diagnosis of locally advanced or metastatic solid tumors:
 - a. who have disease progression on standard therapy,
 - b. who are receiving a standard anticancer treatment but no subsequent approved treatment would be available upon progression,
 - c. who are unable to receive standard therapy, or
 - d. for whom standard therapy does not exist.
2. Demonstrate CCR5 + by IHC (>10% of primary or metastatic tumor cells shows membranous staining and/or high predominance of CCR5+ tumor-infiltrating leukocytes completed at the reference laboratory of [name] at Medical College of Wisconsin).

Note: This test will be done as part of the pre-screening period. It will be performed in archival metastatic tissue. If archival tissue is not available then, fresh biopsy will be done.

3. Be willing to provide tissue from a newly obtained core or excisional biopsy of a tumor lesion (in case archival tissue is not available);
4. Patients must have measurable disease based on RECIST v1.1;
5. ≥ 18 years of age;
6. Patients must exhibit a/an ECOG performance status of 0-1;
7. Life expectancy of at least 6 months;
8. Patients must have adequate organ and bone marrow function within 28 days prior to registration, as defined below:
 - leukocytes $\geq 3,000/\text{mcL}$;
 - absolute neutrophil count $\geq 1,500/\text{mcL}$;
 - platelets $\geq 100,000/\text{mcL}$;
 - total bilirubin: within normal institutional limits;
 - AST(SGOT) & ALT(SPGT) $\leq 2.5 \times$ institutional upper limit of normal (ULN) (applicable to all patients, irrespective of liver disease or metastasis); and
 - creatinine: within normal institutional limits.
9. Clinically normal resting 12-lead ECG at Screening Visit or, if abnormal, considered not clinically significant by the Principal Investigator.

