4.3.1. Treatment Period, T1 (Week 1)

The following assessments will be performed at the first treatment visit of the treatment period:

- Concomitant medications assessment (see [Section 7.5](#)),
- Vital Signs and body weight measurement (see [Section 7.6](#)),
- Physical examination, including evaluation of all body systems (see [Section 7.7](#))
- ECOG Performance Status (see [Section 7.8](#))
- 12-lead Electrocardiogram (see [Section 7.9](#))
- Collection of lab specimens (see [Section 7.11](#)) for
 - Complete blood count

- Biochemistry
- Urine pregnancy test, for female subjects of childbearing potential.
- Urine sample for urinalysis parameters
- CTC and CAML analysis

Note: Complete blood count, biochemistry and urinalysis can be performed within 3 days prior to each visit.

- Leronlimab (PRO 140) Administration (see [Section 6.1.3](#))
- Post Injection Site Evaluation (performed by Investigator) (see [Section 7.13](#))
- Toxicity assessment (see [Section 7.10](#)) and Review of Adverse Events (see [Section 9](#))
- Standard-of-care chemotherapy (see [Section 7.17](#))

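### The planned ORR pools subjects with and without concurrent standard-of-care therapy, and it still counts responses first seen after a later anticancer therapy has started

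*Protocol*

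**What the plan says.** **Objective and regimen.** Protocol 2 gives the primary objective as leronlimab's anti-tumour activity. The Protocol synopsis and SAP 2.6.1 add "as part of a defined treatment protocol". Protocol 3 (repeated in SAP 2.1) says "Subjects participating in this study will be allowed to receive/continue standard-of-care chemotherapy or radiotherapy", and no background regimen is fixed.

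**Who enters.** Inclusion criterion 1 (Protocol 3.3.1) takes subjects "who are receiving a standard anticancer treatment but no subsequent approved treatment would be available upon progression" (1b) as well as those "for whom standard therapy does not exist" (1d). Criteria 1a and 1c add subjects who progressed on standard therapy and subjects who cannot receive it. During the study, Protocol 7.5.2 bars only other investigational agents.

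**Optional or integral.** Protocol 3 permits SOC. Protocol 1.5 speaks of leronlimab "in combination with other chemotherapy agents", Protocol 1.6.2 of leronlimab "in combination with standard-of-care chemotherapy or radiotherapy", and Protocol 4.3.1 lists "Standard-of-care chemotherapy" among the items at the first treatment visit.

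**Response rate.** ORR is CR plus PR over all evaluable subjects (Protocol 8.7.3; SAP 2.7.1 and 7.10.8). The Evaluable Population requires one dose and measurable disease, with no condition on concurrent therapy (Protocol 8.6.1.1, SAP 6.1). SAP 7.9 prespecifies no subgroup and leaves subgroup analyses to be run as needed.

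**Response window.** Protocol 7.15.6 takes the best response from start of treatment to progression or recurrence. Protocol 4.4, 4.4.2 and Table 4-1 footnote 20, with a copy in the SAP Appendix 1 footnotes, keep imaging subjects who stop for an adverse event without progression, and count any response found.

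**The concern.** There are two separate problems.

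First, a reader who sets the reported ORR beside the stated objective will take it as leronlimab's response rate. In a single arm where some subjects are on active chemotherapy or radiotherapy and others have no standard option, one pooled figure cannot say how much of the response arose without SOC. If a split is chosen only after the data are seen, it is open to selection.

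Second, a subject could stop leronlimab for toxicity, start another anticancer therapy before progression, shrink on it, and be counted as a responder. The response would be credited to leronlimab because the written rule says so, not because anyone judged it attributable. Confirming a response shows that it lasts, not what caused it.

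**Working it through.** **No plan figure to reproduce.** The sample size of up to 30 rests on clinical judgment (Protocol 8.2). The plan states no null rate, target ORR or activity threshold, and none is assumed here.

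**Step 1: what the pooled rate can show.** With n0 subjects without SOC and n1 with it, pooled ORR = (n0·p0 + n1·p1)/(n0 + n1). This is one observed number for two unknown rates, and the documents do not give n0 or n1. As an illustration, take 3 responses in 30: 10.0%, exact (Clopper-Pearson) 95% CI 2.1 to 26.5%. The limits are the 2.5% point of Beta(x, n − x + 1) and the 97.5% point of Beta(x + 1, n − x). For x = 0 the upper limit is 1 − 0.025^(1/n); for n = 8 this is 36.9%. The stratum sizes 8, 15 and 22 are assumptions.

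| Assumed n with SOC | Responders placed | Without SOC | With SOC |
|---|---|---|---|
| 8 | all with SOC | 0/22 (0 to 15.4%) | 3/8 (8.5 to 75.5%) |
| 15 | all with SOC | 0/15 (0 to 21.8%) | 3/15 (4.3 to 48.1%) |
| 22 | all with SOC | 0/8 (0 to 36.9%) | 3/22 (2.9 to 34.9%) |
| 8 | all without SOC | 3/22 (2.9 to 34.9%) | 0/8 (0 to 36.9%) |
| 15 | all without SOC | 3/15 (4.3 to 48.1%) | 0/15 (0 to 21.8%) |
| 22 | all without SOC | 3/8 (8.5 to 75.5%) | 0/22 (0 to 15.4%) |

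The same 10.0% fits an observed rate without SOC anywhere from 0% to 37.5% (3/8). The direction is not determined. In every row the two intervals overlap, so a split describes the strata but would seldom separate them.

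**Step 2: where each clock stops.**

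| Item | Ends at | Ends at new anticancer therapy? |
|---|---|---|
| Adverse-event follow-up (Protocol 4.4) | 30 days after last dose | Yes, if a new treatment starts first |
| Best response (Protocol 7.15.6) | Progression or recurrence | No |
| Response after stopping for an adverse event (Protocol 4.4, 4.4.2, Table 4-1 footnote 20; SAP Appendix 1) | Progression | No |

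Protocol 4.4.2 records later anticancer treatment, so the information exists, but no response rule uses it.

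**Step 3: size of the second gap.** One response counted in this way adds 100/30 = 3.3 points to the pooled ORR. In a stratum of 15 it adds 100/15 = 6.7 points (0/15 becomes 1/15, 0.2 to 31.9%). In a stratum of 8 it adds 100/8 = 12.5 points (0/8 becomes 1/8, 0.3 to 52.7%). How often it would happen cannot be derived.

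**Step 4: would a no-SOC stratum be clean?** Criterion 1 sets no washout from standard therapy, and the 28-day rule in exclusion 1 covers only investigational agents and devices. Protocol 4, 4.2.1 and Table 4-1 footnote 8 accept a baseline scan up to 3 months before Screening, while Protocol 7.15 asks for 28 days before registration. On the longer allowance, with up to 28 days from Screening to first dose, a scan could be about four months old. Therapy given between that scan and first dose could produce shrinkage that is scored as response, even in a subject on no SOC at first dose.

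**The case against.** The strongest reply is that the plan never promises a single-agent response rate. Protocol 1.5 and 1.6.2 describe combination use, the synopsis refers to a treatment protocol, and SAP 5 disclaims hypothesis testing and reliable conclusions. A pooled descriptive ORR for leronlimab with or without SOC is a legitimate result. This stands: a reader might infer that the trial fails at a stated monotherapy aim, and the documents do not support that. What remains is that the objective names leronlimab while the rate mixes two kinds of subject without saying so.

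It can also be said that SOC may be received as well as continued, so disallowing every response after therapy started on study would discard responses to the permitted regimen. That is right, and it limits any cut-off in the main ORR to therapy begun after the last leronlimab dose.

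Post-treatment imaging is scheduled only for adverse-event discontinuations without progression, so few responses can enter by that route. This also stands.

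Exclusion 5 lets the investigator keep out subjects whose therapy might confound the results. It is discretionary, and criterion 1b expressly admits subjects on standard treatment, so it does not settle the matter.

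By-subject listings (Protocol 8.6, SAP 10.1) and recorded medications would allow a later split. They would, but not a prespecified one.

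**Conclusion.** The point holds in a limited form. The pooled ORR describes leronlimab with or without SOC and does not show what leronlimab does alone. Independently, the response rules as written count a response first seen after another anticancer therapy has started.

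The first gap concerns labelling and prespecification; it does not make the pooled rate invalid. The second is a real but narrow leak, worth 3.3 points per response at n = 30, with unknown frequency. All split figures rest on assumed SOC shares, and the responders could fall on either side.

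A reader might also infer that reporting subjects without SOC would isolate leronlimab's effect. It would not: there is no control arm or benchmark, no washout from standard therapy, and the baseline scan may predate other treatment.

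**What to change.** 1. **Cut-off after leronlimab.** In Protocol 4.4, 4.4.2, 7.15.6 and Table 4-1 footnote 20, and in SAP 7.10.8 and the matching Appendix 1 footnote, count a response only if it is first documented before any new anticancer therapy started after the last leronlimab dose. The subject stays in the denominator.
2. **SOC started while on leronlimab.** Keep these responses in the main pooled ORR, since the protocol allows such therapy. Add a sensitivity ORR that does not count them.
3. **Descriptive split.** In SAP 7.9 and 8.2.1, prespecify ORR with exact 95% CIs by concurrent anticancer therapy at first dose: none, or ongoing or starting with the first dose. Label the pooled rate *leronlimab with or without SOC*. In the *none* stratum, do not count a response first seen after SOC starts, and flag any responder who had anticancer therapy between the baseline scan and first dose. Do not present this stratum as isolating leronlimab.
4. **Reconcile.** Settle whether SOC is optional or integral (Protocol 1.5, 1.6.2, 3, 3.3.1, 4.3.1) and how old the baseline scan may be (Protocol 4, Table 4-1 footnote 8, 7.15).

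**Cost.** No new data are needed: treatment start and stop dates (Protocol 7.5) and later anticancer treatment (Protocol 4.4.2) are already recorded. The SAP is still a first draft. The response rule needs a protocol amendment with IRB approval (Protocol 11.3). The price is small strata with wide intervals (0/8 gives 0 to 36.9%) and a possibly lower ORR.

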3.1 STUDY CENTER

Up to 10 centers in the United States (US).

3.2 STUDY POPULATION

The target population for this study is subjects with histologically or cytologically confirmed diagnosis of CCR5+ locally advanced or metastatic solid tumors.

This will be a multicenter trial. A total of 30 subjects will be needed for this trial.

Eligibility will be evaluated by the study team according to the following criteria. Eligibility waivers are not permitted. Subjects must meet all of the inclusion and none of the exclusion criteria to be registered to the study.

3.3 ELIGIBILITY CRITERIA

3.3.1. Inclusion Criteria

Subjects are required to meet all of the following criteria for enrollment into the study:

1. Must have a histologically or cytologically confirmed diagnosis of locally advanced or metastatic solid tumors:
 - a. who have disease progression on standard therapy,
 - b. who are receiving a standard anticancer treatment but no subsequent approved treatment would be available upon progression,
 - c. who are unable to receive standard therapy, or
 - d. for whom standard therapy does not exist.
2. Demonstrate CCR5 + by IHC (>10% of primary or metastatic tumor cells shows membranous staining and/or high predominance of CCR5+ tumor-infiltrating leukocytes completed at the reference laboratory of [name] at Medical College of Wisconsin).

Note: This test will be done as part of the pre-screening period. It will be performed in archival metastatic tissue. If archival tissue is not available then, fresh biopsy will be done.

3. Be willing to provide tissue from a newly obtained core or excisional biopsy of a tumor lesion (in case archival tissue is not available);
4. Patients must have measurable disease based on RECIST v1.1;
5. ≥ 18 years of age;
6. Patients must exhibit a/an ECOG performance status of 0-1;
7. Life expectancy of at least 6 months;
8. Patients must have adequate organ and bone marrow function within 28 days prior to registration, as defined below:
 - leukocytes $\geq 3,000/\text{mcL}$;
 - absolute neutrophil count $\geq 1,500/\text{mcL}$;
 - platelets $\geq 100,000/\text{mcL}$;
 - total bilirubin: within normal institutional limits;
 - AST(SGOT) & ALT(SPGT) $\leq 2.5 \times$ institutional upper limit of normal (ULN) (applicable to all patients, irrespective of liver disease or metastasis); and
 - creatinine: within normal institutional limits.
9. Clinically normal resting 12-lead ECG at Screening Visit or, if abnormal, considered not clinically significant by the Principal Investigator.
10. Females of child-bearing potential (FOCBP) and males must agree to use two medically accepted methods of contraception with hormonal or barrier method of birth control, or abstinence, prior to study entry, for the duration of study participation and for 60 days after the last dose of study drug (Refer to Appendix 1). Should a female patient become pregnant or suspect she is pregnant while participating in this study, she should inform her treating physician immediately. NOTE: A FOCBP is any woman (regardless of sexual orientation, having undergone a tubal ligation, or remaining celibate by choice) who meets the following criteria:
 - Has not undergone a hysterectomy or bilateral oophorectomy; and
 - Has had menses at any time in the preceding 12 consecutive months (and therefore has not been naturally postmenopausal for > 12 months).

11. FOCBP must have a negative serum pregnancy test at Screening Visit and negative urine pregnancy test prior to receiving the first dose of study drug; and
12. Patients must have the ability to understand and the willingness to sign a written informed consent prior to registration on study.

3.3.2. Exclusion Criteria

Subjects meeting any of the following criteria will be excluded from enrollment:

1. Is currently participating and receiving study therapy or has participated in a study of an investigational agent and received study therapy or used an investigational device within 28 days prior to enrollment;
2. Patients who have a history of allergic reactions attributed to compounds of similar chemical or biologic composition to leronlimab (PRO 140) are not eligible;
3. Patients who have had prior exposure to CCR5 antagonists are not eligible;
4. Has known active central nervous system (CNS) metastases and/or carcinomatous meningitis. Note: Subjects with previously treated brain metastases may participate provided they are stable (without evidence of progression by imaging for at least four weeks prior to the first dose of trial treatment and any neurologic symptoms have returned to baseline), have no evidence of new or enlarging brain metastases, and are not using steroids for at least 7 days prior to trial treatment. This exception does not include carcinomatous meningitis which is excluded regardless of clinical stability;
5. Has a history or current evidence of any condition, therapy, or laboratory abnormality that might confound the results of the trial, interfere with the subject's participation for the full duration of the trial, or is not in the best interest of the subject to participate, in the opinion of the treating investigator;
6. Has known psychiatric or substance abuse disorders that would interfere with cooperation with the requirements of the trial; and
7. Is pregnant or breastfeeding, or expecting to conceive or have children within the projected duration of the trial, starting with the pre-screening or screening visit through the duration of study participation.

